## Background and Rationale

### Interferon gamma (IFN $\gamma$ ) in secondary HLH

HLH is a syndrome of severe immune activation and deregulation characterized by hyperactive macrophages and lymphocytes, pro-inflammatory cytokine hypersecretion, hemophagocytosis, and tissue and organs damage. HLH occurs as either a primary (pHLH, familial) or secondary (sHLH, sporadic) disorder (Henter et al., 1998; Janka, 1983). pHLH is an autosomal recessive disease with an incidence of 1/50,000 live-born children (Henter et al. 1991; Arico et al. 1996). Patients often have a clear familial inheritance or genetic mutation. pHLH is caused by homozygous mutations in the genes coding for perforin, Munc13-4, syntaxin 11, Munc18-2 and other proteins involved in cytotoxic granule activation, polarization, priming, fusion, or function (Jordan et al., 2011; Zhang et al., 2014). These mutations result in defective immune effector cell function, uncontrolled activation of histiocytes, and pathognomonic clinical manifestations of HLH. Secondary HLH often occurs as a result of pathological immune activation in response to a trigger. Frequently noted triggers include malignancies (especially hematological malignancies including acute leukemia's and lymphomas), infections (especially EBV) and rheumatologic disorders (sJIA, SLE). The list of triggers associated with secondary HLH is extensive (Henter et al., 1997). Primary HLH is reported to be more frequent in childhood.

The pathogenesis of secondary HLH remains a matter of debate. Reports have recently described patients developing Macrophage Activation Syndrome (MAS) in the context of systemic juvenile idiopathic arthritis (sJIA). These patients were identified to be heterozygous for rare variants in the primary HLH-associated genes (Zhang et al., 2014) highlighting potential etiological, clinical, and pathological similarities between familial and acquired forms of HLH. A link between mutations in the perforin gene and predisposition to hematological malignancies has been described (Clementi et al., 2005; Zhang et al., 2014), further supporting a possible contribution of hypomorphic mutations in HLH-related genes to the development of M-HLH (Lehmberg 2015).

Immune-activation and immune mediated pathology likely play a central role in the evolution of HLH. Secondary HLH is characterized by acute clinical signs and symptoms of immune activation including hepatomegaly, jaundice, adenopathy, rash, seizures, and focal neurologic

Protocol NI-0501-07 version 1.0, dated 12 Feb 2016

deficits as well as laboratory measures such as strikingly high serum levels of numerous cytokines including interferon gamma (IFN $\gamma$ ), tumor necrosis factor  $\alpha$  (TNF- $\alpha$ ), interleukin 6 (IL-6), IL-10, and macrophage–colony-stimulating factor (M-CSF) (Akashi et al., 1994; Ohga et al., 1993). Furthermore, biopsies of lymphoid tissues or histological examination of liver tissue from HLH patients reveal highly activated macrophages and lymphocytes, further supporting striking activation of the immune system. Secondary HLH carries a significant mortality rate with approximately 10 to 30% of the diagnosed patients succumbing from the disease (Celkan et al., 2009; Minoia et al., 2014; Grom et al., submitted). Categorizing patients into primary or secondary HLH based on clinical manifestations is often difficult and may be of limited value. Treatment should be initiated expediently if the diagnosis of HLH is suspected, regardless of the classification/trigger.

Secondary HLH that develops in the setting of malignancy is also known as malignancy-associated hemophagocytic lymphohistiocytosis (M-HLH). The majority of malignancies triggering secondary HLH in children and adults are lymphomas and leukemia. While primary forms of HLH are more common in younger patients, M-HLH is more frequent in adults (Ramos-Casals et al., 2014). Machaczka et al. (2011) estimated that HLH affects 0.9% of adults with hematological cancer, but the prevalence may be as high as 20% in patients with specific types of B-cell lymphoma's (intravascular B-cell lymphoma or B-cell lymphoma without peripheral adenopathies) and T-cell lymphoma (nasal natural-killer-cell or panniculitis-like subtypes) (Ramos-Casals et al., 2014).

M-HLH may manifest during the treatment (iatrogenic) of a known malignancy or as the presenting feature of a yet undiagnosed malignancy (non-iatrogenic). It is postulated that the hyperinflammation is triggered by the neoplasm or its treatment, due to an excessive secretion of pro-inflammatory cytokines by the malignant cells or by T-cell activating immunotherapies for the treatment of leukemia/lymphoma and emerging for treatment of solid tumors (e.g. bispecific monoclonal antibody blinatumomab, CAR T-cell therapies) (Hijiya et al., 2005; Teachey et al., 2013; Lee et al., 2014).

The malignancy induced immunodeficiency combined with therapy likely predisposes to infections and defective T-/NK-cell function reducing the threshold for triggering HLH in these

patients (Celkan et al., 2009). Indeed, similarly to primary HLH, infections are often identified as co-triggers in iatrogenic M-HLH.

The clinical course of M-HLH is often aggressive, and characterized by poor outcome, which are further impacted by the nature and status of the underlying malignancy. A single center retrospective study in adults reported only 1 of 8 patients survived despite identification of HLH and implementation of HLH directed therapies (Machaczka et al., 2011). A recent retrospective study in children and adolescents (n=27) reported a 6-month survival rate of 67% in non-iatrogenic M-HLH and 63% in iatrogenic M-HLH (Lehmberg et al., 2015). The group at MD Anderson Cancer Center retrospectively identified pathologic hemophagocytosis and/or lymphohistiocytosis in 61 adult patients with underlying malignancies between 1991-2001. Thirty five patients had additional systemic variables conferring a high suspicion for M-HLH. The median survival among the 35 patients was a dismal 1.5 months. The median survival was 1.2 months among patients treated with HLH directed therapy as compared to 1.8 months among those not treated with HLH directed therapies. 31% of patients were alive at 6-months (Tamamyam, Daver et al.; manuscript submitted).

An effective therapeutic approach to M-HLH (iatrogenic and non-iatrogenic) remains unknown. Of note is that agents that are currently considered as standard therapies for HLH (corticosteroids, etoposide) are often part of the treatment of malignancies known to be able to cause M-HLH. Furthermore, the addition of etoposide, alemtuzumab, dexamethasone may induce worsening myelosuppression and immunodeficiency in patients who have an underlying malignancy and/or recent systemic therapy. A non-myelosuppressive and less immunosuppressive therapy would be an ideal approach to evaluate in M-HLH patients. A prompt initiation of an HLH-directed regimen (before or in combination with the malignancy-directed therapy) is of critical importance to decrease the high mortality rate in these patients. Furthermore, studies have described the use of tocilizumab, an anti-IL-6R antibody, to manage cytokine release syndrome occurring after treatment with T-cell engaging therapies (Barrett et al., 2014).

NI-0501 is a fully human anti-interferon gamma (IFN $\gamma$ ) monoclonal antibody (mAb) that binds to and neutralizes IFN $\gamma$ . NovImmune is developing NI-0501 as the first targeted monoclonal therapy for HLH. Several lines of evidence support the investigation and use of therapeutic agents targeting IFN $\gamma$  in HLH:

Protocol NI-0501-07 version 1.0, dated 12 Feb 2016

1. Two animal models of pHLH and two animal models of sHLH have been investigated in the context of the NI-0501:

- Perforin knockout mice and Rab27-deficient mice develop all the diagnostic and many of the clinical and laboratory characteristics of human primary HLH when infected with lymphocytic choriomeningitis virus (LCMV) as a trigger. Neutralization of the high circulating IFN $\gamma$  levels in both animal models led to the reversal of HLH clinical and laboratory abnormalities, and dramatically improved survival in the animal model characterized by high mortality (pfp  $-/-$  mice) (Pachalopnik Schmid et al., 2009, Jordan et al., 2004).
- Repeated administration of CpG, causing TLR9 stimulation, has been used to mimic a chronic severe hyperstimulation in healthy mice as a model of HLH secondary to infection. Although these mice do not necessarily die, they develop typical clinical and laboratory features of HLH (Behrens et al., 2011). Administration of an anti-IFN $\gamma$  antibody led to reversal of clinical and laboratory features of HLH. Importantly, in this model it was demonstrated that administration of the anti-IFN $\gamma$  antibody also led to full neutralization of IFN $\gamma$  effects in relevant target tissues, such as liver and spleen (Buatois et al, submitted).
- To study the physiopathology of sHLH in the context of rheumatic diseases, an animal model has been generated using IL-6 transgenic mice expressing high levels of IL-6, to mimic what occurs in patients with sJIA. When triggered with TLR ligands, these mice die with many of the features of the human HLH (Stippoli et al. 2012). In these mice, when IFN $\gamma$  was neutralized by administration of an anti-IFN $\gamma$  antibody, survival was markedly improved and HLH laboratory parameters reverted.

In conclusion, in all presented animal experiments, IFN $\gamma$  was demonstrated to be a key pathological effector in disease onset and progression.

2. Primary and secondary HLH patients have hypercytokinemia with elevated levels of several pro-inflammatory cytokines including IFN $\gamma$  (Henter et al., 1991; Janka et al., 1998; Xu et al. 2012). More recently, high levels of IFN $\gamma$  were demonstrated both in patients with HLH secondary to infections and in sJIA patient developing MAS (Buatois et al., manuscript

submitted; Bracaglia et al. manuscript submitted). The levels of CXCL9, CXCL10 and CXCL11, three chemokines known to be induced by IFN $\gamma$ , were also significantly elevated. Noteworthy, levels of IFN $\gamma$  and of the three IFN $\gamma$ -inducible chemokines were found to significantly correlate with laboratory parameters of disease severity, such as ferritin, platelet count and transaminases.

3. A Phase 2 pilot study is presently ongoing to evaluate the efficacy and safety of treatment with NI-0501, an anti-IFN $\gamma$  monoclonal antibody, in pHLH. Based on data gathered so far, NI-0501 treatment has been well tolerated and shown a favorable impact on all relevant clinical and laboratory features of HLH such as fever, splenomegaly, cytopenia, hyperferritinemia, hypofibrinogenemia, and also CNS signs/symptoms (Jordan et al, 2015).

No animal models specific to M-HLH have been described (Brisse et al., 2015). The levels of IFN $\gamma$  and other pro-inflammatory cytokines at diagnosis and their correlation with clinical evolution and severity of the HLH manifestations during and after therapy have been poorly characterized for M-HLH. The fact that primary HLH and HLH secondary to inflammatory/autoimmune diseases or infections have many pathophysiological and clinical features in common with M-HLH, suggests that IFN $\gamma$  might also play a key role in M-HLH. The present observational study is designed to provide a better understanding of the potential use of IFN $\gamma$  and IFN $\gamma$ -inducible chemokines as markers of M-HLH disease activity and potential prognosis and of the possible role of IFN $\gamma$  as a therapeutic target in M-HLH, and to explore the genetic profiles in patients with M-HLH with regard to HLH-related genes.

---

Study Objectives:	

• To determine the levels of inflammatory markers including, but not limited to interferon gamma (IFN<math>\gamma</math>), interleukin 1 beta (IL-1<math>\beta</math>), interleukin 6 (IL-6), interleukin 10 (IL-10), interleukin 17 (IL-17), soluble IL-2 Receptor <math>\alpha</math> (sCD25), C-X-C chemokine ligand 9 (CXCL9), C-X-C chemokine ligand 10 (CXCL10), C-X-C chemokine ligand 11 (CXCL11), soluble CD163 (sCD163), neopterin and Tumor Necrosis Factor alpha (TNF<math>\alpha</math>) in patients diagnosed with M-HLH and whenever possible, to monitor the evolution over time of these markers.

• To assess the relationship between the above mentioned inflammatory cytokines and disease activity.

• To assess the relationship between genetic variants of the genes typically causing primary HLH and M-HLH and associated inflammatory markers.

Sample Size:	A minimum of 14 (maximum of 50) M-HLH patients will be studied, including a minimum of 7 non iatrogenic M-HLH and 7 iatrogenic M-HLH. A control group of 10 patients with a diagnosis of hematological malignancy in absence of HLH will also be evaluated.
Study Population:	
Male and female (adult and children) patients who are diagnosed with M-HLH and that meet the inclusion criteria listed below.
 
In addition, patients with a diagnosis of hematological malignancy in the absence of HLH will be included as a control group.

Inclusion Criteria:	

1. Patients diagnosed with HLH in the context of a malignancy. The diagnosis of M-HLH will be established by the treating physician.

2. The patient or patient's legal representative (in case the patient is < 18 years old) must have consented to the use of their clinical data for research purposes at the site.

3. For the control group, patients with a diagnosis of hematological malignancy and never diagnosed with HLH or no suspicion of HLH (at any time, including time after sample collection in case of use of retrospective sample).

Study Design:	This is a non-interventional study designed to determine the levels of pro-inflammatory markers (as listed above) in patients diagnosed with M-HLH and to assess the relationship between the biomarkers

---

Protocol NI-0501-07 version 1.0, dated 12 Feb 2016

---

and disease activity and prognosis during the M-HLH course. Inflammatory markers will also be measured in a group of control patients diagnosed with hematological malignancy in absence of HLH (as described above).

Data collection may be performed retrospectively if sufficient clinical information is available to allow for a meaningful interpretation of the biomarker results.

An approximate volume of 500 µl – 1 ml of serum or plasma is required per time point. Whenever possible, serum (and not plasma) should be collected, as this is the preferred matrix for the biomarker analysis.

In addition to the serum samples for the biomarker analysis, relevant information gathered by the treating physician will be collected in a data collection form. This will include information on the clinical presentation of M-HLH, the type of underlying malignancy, the date of onset of malignancy in relation to HLH manifestations, treatment regimen prior to and/or ongoing at the time of M-HLH onset, laboratory parameters, M-HLH disease activity (e.g. newly diagnosed, reactivation), specific HLH therapy with best response to the therapy, other concomitant medications, patient follow-up and disposition, stem cell transplant status, duration of response, and survival. Whenever possible, collection of serum samples for biomarker analysis and relevant information should occur at M-HLH diagnosis, at regular time intervals during the treatment course, at resolution and/or reactivation of the disease.

In addition to the above a minimum of 1 ml of whole blood will be collected (EDTA tubes) for genetic characterization and identification of the presence of genetic variants of the genes typically causing primary HLH. A specific consent for genetic testing must be given by the patient. Genetic samples may also be collected from existing bank of samples (frozen whole blood in EDTA or frozen extracted DNA), if proper consent has been obtained.

---

**Study Duration:**

This study collects information on M-HLH patients at diagnosis and during treatment of the disease, and will last until a minimum of 14 (maximum of 50), including at least 7 iatrogenic and 7 non-iatrogenic M-HLH patients and up to 10 hematological malignancy patients in absence of HLH have been recruited.

---

**Exploratory Parameters:**

**1. Laboratory parameters**, at the time of sample collection, assessed at the local laboratory, according to local clinical practice, such as:

---

- Hemoglobin, Hematocrit, Red blood cells, white blood cells and differential count, platelets
- Fibrinogen
- Ferritin
- Fasting triglycerides
- AST, ALT, Alkaline Phosphatase
- BUN, serum creatinine
- Albumin (if available)
- Sodium (if available)
- Beta2 microglobulin (if available)
- Serum IgG levels (if available)
- Lactate dehydrogenase
- Total and conjugated Bilirubin
- D-dimers
- CRP
- NK-cell activity (if available)

**2. Inflammatory markers of disease activity.** The following assessments will be performed by the NovImmune Bioanalytical Assay Laboratory:

- IFN $\gamma$
- sCD25
- IL-1 $\beta$ , IL-6, IL-10, IL-17
- TNF $\alpha$
- CXCL9, CXCL10, CXCL11
- sCD163 and neopterin

**3. Additional parameters recorded at the time of diagnosis** will be collected when available for *a posteriori* diagnosis:

- Temperature
- Splenomegaly
- Hb concentration
- Platelet and neutrophils count
- Triglycerides

---

---

- Fibrinogen
- Hemophagocytosis
- NK cell activity
- Ferritin
- sCD25

---

**Statistical Analysis:**

All analyses are exploratory. Statistical analyses of the data collected in this study will be focused on providing tabular and graphical summaries of the levels of inflammatory markers and of the clinical features of the disease both at diagnosis and during the course of treatment. Levels of inflammatory markers will be compared between patients with active M-HLH and the control group (i.e. hematological malignancy in absence of HLH). In addition, the degree of correlation between inflammatory markers, and between inflammatory markers and the severity of clinical manifestations, response to therapy, and survival of the patients will be assessed. Analyses may also be performed to study these relationships in various subgroups of patients, depending on the demographic, genetic and clinical characteristics observed, including *a posteriori* diagnosis based on HLH-2004 diagnostic criteria (Henter et al., 2007).

Criteria for diagnosis are:

- i) Fever
- ii) Splenomegaly
- iii) Cytopenia (affecting  $\geq 2$  of 3 lineages in peripheral blood):
  - Hb  $<90$  g/L (in infants  $< 4$  weeks: Hb  $<100$  g/L)
  - Platelets  $<100 \times 10^9$ /L
  - Neutrophils  $<1.0 \times 10^9$ /L
- iv) Hypertriglyceridemia and/or hypofibrinogenemia: Fasting triglycerides  $\geq 3.0$  mmol/L; Fibrinogen  $\leq 1.5$  g/L
- v) Hemophagocytosis in bone marrow or other specimens
- vi) Low or absence NK-cell activity (according to local laboratory reference)
- vii) Ferritin  $\geq 500$   $\mu$ g/L
- viii) sCD25  $\geq 2400$ U/ml

---

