1 Abbreviations and definition of terms

AE	Adverse event
CSR	Clinical Study Report
FAS	Full Analysis Set
IFN γ	Interferon gamma
ICF	Informed consent form
LLOQ	Lower limit of quantification
HLH	Hemophagocytic lymphohistiocytosis
M-HLH	Malignancy-associated hemophagocytic lymphohistiocytosis
NI-0501	Emapalumab
pHLH	Primary hemophagocytic lymphohistiocytosis
SAE	Serious adverse event
SAP	Statistical Analysis Plan
Sobi	Swedish Orphan Biovitrum
ULOQ	Upper limit of quantification
PPS	Per Protocol Set

2 Introduction

This Statistical Analysis Plan (SAP) describes the planned analysis and reporting for Sobi protocol NI-0501-07 (An observational, multicenter study to evaluate interferon gamma (IFN γ) and other inflammatory mediators in patients with malignancy-associated hemophagocytic lymphohistiocytosis (M-HLH)).

This observational study is designed to provide a better understanding of the potential use of IFN γ and IFN γ -inducible chemokines as markers of M-HLH disease activity and potential prognosis and of the possible role of IFN γ as a therapeutic target in M-HLH, and to explore the genetic/ profiles in patients with M-HLH with regard to HLH-related genes in patients who are diagnosed with M-HLH.

The purpose of this SAP is to outline the exploratory analyses to be completed to support the synopsis for protocol NI-0501-07. The exploratory analyses identified in this SAP could be included in regulatory submissions and/or future manuscripts. Also, additional exploratory analyses not necessarily identified in this SAP may be performed to support the clinical

development program. Any post-hoc analyses not identified in this SAP will be clearly identified as such in the synopsis.

The structure and content of this SAP provides sufficient detail to meet the requirements identified by the FDA and International Conference on Harmonisation of Technical Requirements for Registration of Pharmaceuticals for Human Use (ICH): Guidance on Statistical Principles in Clinical Trials. All work planned and reported for this SAP will follow internationally accepted guidelines, published by the American Statistical Association and the Royal Statistical Society, for statistical practice.

3 Study objectives and endpoints

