3.1 Study objectives

- To determine the levels of inflammatory markers including, but not limited to interferon gamma (IFN γ), interleukin 1 beta (IL1 β), interleukin 6 (IL-6), interleukin 10 (IL-10), interleukin 17 (IL-17), soluble IL-2 Receptor α (sCD25), C-X-C chemokine ligand 9 (CXCL9), C-X-C chemokine ligand 10 (CXCL10), C-XC chemokine ligand 11 (CXCL11), soluble CD163 (sCD163), neopterin and Tumor Necrosis Factor alpha (TNF α) in patients diagnosed with M-HLH and whenever possible, to monitor the evolution over time of these markers.
- To assess the relationship between the above-mentioned inflammatory cytokines and disease activity.
- To assess the relationship between genetic variants of the genes typically causing primary HLH and M-HLH and associated inflammatory markers.

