4.1 Overall study design and plan

This is a non-interventional study designed to determine the levels of pro-inflammatory markers (as listed above) in patients diagnosed with M-HLH and to assess the relationship between the biomarkers and disease activity and prognosis during the M-HLH course. Inflammatory markers will also be measured in a group of control patients diagnosed with hematological malignancy in absence of HLH (as described above).

Data collection may be performed retrospectively if sufficient clinical information is available to allow for a meaningful interpretation of the biomarker results.

An approximate volume of 500 µl – 1 ml of serum or plasma is required per time point. Whenever possible, serum (and not plasma) should be collected, as this is the preferred matrix for the biomarker analysis.

In addition to the serum samples for the biomarker analysis, relevant information gathered by the treating physician will be collected in a data collection form. This will include information on the clinical presentation of M-HLH, the type of underlying malignancy, the date of onset of malignancy in relation to HLH manifestations, treatment regimen prior to and/or ongoing at the time of M-HLH onset, laboratory parameters, M-HLH disease activity (e.g. newly diagnosed, reactivation), specific HLH therapy with best response to the therapy, other concomitant medications, patient follow-up and disposition, stem cell transplant status, duration of response, and survival. Whenever possible, collection of serum samples for biomarker analysis and relevant information should occur at M-HLH diagnosis, at regular time intervals during the treatment course, at resolution and/or reactivation of the disease.

In addition to the above a minimum of 1 ml of whole blood will be collected (EDTA tubes) for genetic characterization and identification of the presence of genetic variants of the genes typically causing primary HLH. A specific consent for genetic testing must be given by the patient. Genetic samples may also be collected from existing bank of samples (frozen whole blood in EDTA or frozen extracted DNA), if proper consent has been obtained.

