5.2 Analyses and reporting

All final analyses identified in the protocol and in this SAP will be performed only after the database lock. A data review will be held prior to database lock. The SAP will be finalized, locked and signed prior to database lock.

Any post-hoc analyses included in the study synopsis which were not identified in this SAP, will be clearly identified as such in the relevant report section.

6 Sample size determination

No formal sample size was calculated for this observational study.

The protocol stated a minimum of 14 (maximum of 50) M-HLH patients will be studied, including a minimum of 7 non iatrogenic M-HLH and 7 iatrogenic M-HLH. A control group of 10 patients with a diagnosis of hematological malignancy in absence of HLH will also be evaluated.

A total of 39 patients were included in the study, 19 patients were diagnosed with M-HLH and 20 patients were included in the control group.

7 Analysis populations

The All enrolled set will be used in the statistical analyses as no study drug was administered.

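### The SAP defines no output for markers over time, by response or by survival, although the protocol plans all three, and section 14 does not declare the gap

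*Protocol*

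**What the plan says.** **Protocol, Statistical Analysis.** Tables and graphs are to cover "levels of inflammatory markers and of the clinical features of the disease both at diagnosis and during the course of treatment". The same paragraph commits to correlating markers with one another and with "the severity of clinical manifestations, response to therapy, and survival of the patients will be assessed". These are firm commitments; only the subgroup work in that paragraph is optional. All analyses are labelled exploratory.

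**SAP aims.** Section 2 says the study should inform the use of IFNγ and its induced chemokines "as markers of M-HLH disease activity and potential prognosis". Section 3.1 keeps the objective, "whenever possible, to monitor the evolution over time of these markers". Section 4.1 describes the study as designed "to assess the relationship between the biomarkers and disease activity and prognosis during the M-HLH course". It lists best response to HLH therapy among the data to be collected, along with "patient follow-up and disposition, stem cell transplant status, duration of response, and survival".

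**SAP outputs.** Sections 12.1 and 13.2 plot one value per HLH patient (closest to diagnosis, and after it) and add summaries by group. Section 12.2 plots markers against each other and four named markers against laboratory values, using the marker value closest to diagnosis. Section 10.2 tabulates clinical features as medical history. Section 8 lists all data by patient.

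**SAP section 14.** Two changes from the protocol are declared: no data for CXCL11 and IL-17, and no genetic analysis because only 5 of 19 HLH patients had data.

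**The concern.** The SAP carries forward the aims and the data collection but not the analyses that connect them. Followed as written, it would yield no summary of how markers change after diagnosis, and nothing that sets a marker beside response or survival. The prognosis purpose and the over-time objective would go unanswered without explanation.

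Section 14 is where a reader looks for departures from the protocol. Its two entries suggest that everything else is intact. For genetics it gives a reason (too few patients); for time course, response and survival it gives neither a statement nor a reason.

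There is also a labelling problem if the analyses are added later. Section 2 says: "Any post-hoc analyses not identified in this SAP will be clearly identified as such in the synopsis". Analyses that the protocol planned could then be reported as post hoc only because the SAP did not define them.

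**Working it through.** No arithmetic applies: the SAP calculates no sample size and presents no tests. The check sets each planned item beside the SAP's defined outputs and its declared changes.

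| Planned in the protocol's Statistical Analysis section | Output defined in the SAP | Declared in section 14 |
|---|---|---|
| Markers at diagnosis | Plots and group summary, 12.1 | Not needed |
| Markers in M-HLH beside controls | Side by side, descriptive, 12.1 | Not needed |
| Marker against marker | Scatter plots, 12.2 item 1 | Not needed |
| Markers during treatment | None | No |
| Markers against response | None | No |
| Markers against survival | None | No |
| Markers against severity of manifestations | Laboratory values only, 12.2 item 2 | No, but stated in 3.2.2 |

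I then looked for anything in the SAP that could fill the three empty rows.

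1. *HLH plots in 12.1, 12.2 and 13.2.* When a patient has several samples, one value is used. The plots therefore cannot show change.
2. *Group summaries in 12.1 and 13.2.* They are split by HLH, non-HLH and overall, with no visit, window or change from diagnosis. Even if serial samples were pooled into them, that would not be a display over time.
3. *Control minimum and maximum.* These have no time axis and do not concern the M-HLH course.
4. *Three-day window in 12.2.* It pairs the samples being correlated and adds no later time point.
5. *Clinical features in 10.2.* They are counted but not related to any marker.
6. *Endpoints in 3.2.* They cover marker levels, correlations among markers and with laboratory values, and genetic variants. There is no response or survival endpoint.
7. *Listings in section 8.* Serial values and recorded outcomes would appear here, but a listing is not the summary or correlation that the protocol describes.
8. *Section 5.2.* It says: "All final analyses identified in the protocol and in this SAP will be performed only after the database lock". This presupposes that protocol analyses remain, but it fixes timing and defines no output.

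None of these fills the time-course, response or survival rows.

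**The case against.** The best defence is that this is a small exploratory study whose SAP supports a synopsis. Section 2 allows further exploratory analyses, 5.2 still refers to analyses in the protocol, and every value will be listed. The over-time objective applies only where possible, and none of the three listed objectives names prognosis, response or survival; those come from the purpose and design text and the protocol's analysis section. Much of this stands, and it limits the consequence. It does not supply an output or explain the absence. If data were too sparse, section 14 could say so, as it does for genetics.

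Several stronger readings are tempting but unsupported:

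- *The analyses were withdrawn, or selectively omitted.* The documents do not show this. They leave open whether the analyses were dropped, lacked data or were merely left undefined.
- *Section 8 restricts the displays to those in the SAP.* Its wording introduces the format of descriptive statistics. It does not decide which analyses exist.
- *Section 12.4 forbids the missing analyses.* It concerns subgroups. A profile over time is not a subgroup analysis, and relating a marker to an outcome need not be one.
- *Severity was dropped silently.* Section 3.2.2 says openly that disease activity is represented by laboratory assessments and that selected markers are used. The protocol's background also treats ferritin, platelets and transaminases as severity parameters. What remains is that section 14 omits the narrowing.
- *A fixed fraction of the protocol's analyses is missing.* Any such fraction depends on how one paragraph is divided, so the table above should not be read as a score.

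**Conclusion.** The point holds for time course, response and survival: three analyses stated firmly in the protocol have no defined table, figure or correlation in the SAP, and none appears among the two changes in section 14. The narrowing of severity to laboratory values is a lesser note about disclosure.

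The effect is on completeness and transparency. No error rate or confirmatory conclusion is involved, since all analyses are exploratory and no tests are presented. With 19 HLH patients, any added display will be imprecise.

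The conclusion rests on the SAP text as available; figures not shown were not used as evidence. Whether serial samples, response and survival were actually recorded is not stated, so the remedy has to be conditional. This should be corrected, at modest priority.

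**What to change.** Amend the SAP before database lock, the point by which 5.2 requires it to be final.

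1. *Where serial samples exist*, add to section 12 per-patient marker profiles on a log scale against days from HLH diagnosis. Values below the quantification limit are already replaced by half that limit (8.4.2), so they can be plotted. State that days from diagnosis only approximates the treatment course, because section 11 keeps medication as uncoded free text.
2. *Where outcomes were recorded*, show the marker value chosen by the 12.1 rule as individual points with median and quartiles, by survival status and by best response. Name the 12.1 rule explicitly, because 12.2 does not require the value to follow diagnosis. Show each value's days from diagnosis, since 12.1 sets no maximum interval. Give follow-up time from that sample, because a patient must be alive to be sampled. Neither document defines response categories, so use those recorded on the data collection form and list them before lock.
3. *State* that these displays are descriptive and are not the subgroup analyses excluded by 12.4.
4. *For each planned analysis that the data cannot support*, and for the narrowing of severity to laboratory values, add to section 14 that the protocol planned it, that it is not performed or is limited, and why.

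The minimum cost is one paragraph in section 14. The maximum is one set of profile plots, a few grouped point plots and a clarifying sentence. The downside is a handful of extra descriptive outputs that will be imprecise once 19 patients are divided by outcome.
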